### **Treatment with NAC:**

For this single center randomized double-blind placebo controlled, prospective, Phase II study, each subject will be dosed with approximately 70 mg/kg/day of NAC for 8 weeks. To facilitate drug compounding, three tiers of drug dose will be administered based on body weight as described in **Table 3**.

**Table 3: NAC Dosing**

Participant's weight (kg)	Dose (BID)
< 20	700 mg
20-40	1050 mg
> 40	1350 mg

\*Max dose not to exceed 2700mg/day (1350mg BID)

We have treated 5 patients off-label with NAC at 900 mg twice daily with improved behaviors without side effects. NAC is a natural supplement that acts as an antioxidant and a glutamate modulating agent. It is widely available over the counter. We have received IND approval from the FDA to use NAC for the application in this study (IND# 139468).

To mitigate potential non-compliance, participants will be given a 'test dose' of the study placebo (capsule and/or powder) at the screening visit. If prescribed encapsulated drug, they will have to demonstrate that they can swallow the capsule. If prescribed powder, they will have to demonstrate that they can drink the powder without any issues.

### **Blood Acquisition and Storage:**

Blood will be collected per institutional practice after participants are recruited and consented. No more than 3 ml of blood per kg of body weight will be collected during any single blood draw. No more than 5% of the patient's estimated blood volume will be taken for both clinically indicated and research purposes within a 24-hour time period. Samples will be logged and stored in the Cincinnati Children's Biobank.

### **Collection/use/disclosure of video recordings.**

Certain study assessments (i.e.: PANESS) will be recorded using a tripod mounted video camera or similar device. The recorded assessment will be reviewed by multiple trained personnel to standardize grading across participants and improve the precision and accuracy of the scores. These records may be used for purposes of study, research, and teaching. If a clinically significant phenotype is noted in the recording that would benefit the scientific and clinical communities, portions of the recorded assessment may be published in scientific journals or presented at scientific conferences. The participant's/family's name will not be used. Information about the intention to record a portion of the study visits will be outlined in the consent form. Authorization is given when the consent form is signed by the participant/family.

### **Physical and Neurological Examination for Subtle Signs (PANESS) scale $\psi$ :**

At present, there are no clinical characteristics, neuropsychologic variables, phenotypic variants or biomarkers known to accurately predict treatment response of abnormal motor/learning behaviors in NF1 to NAC therapy.

Therefore, the primary outcome of the proposed study is motor function rated with the PANESS, a validated scale that consistently demonstrates significant impairments in children with ADHD, and which our preliminary data suggest may demonstrate more extreme problems in children with NF1.

The PANESS test measures timed movements, lateral preference, motor overflow, dysrhythmia, coordination, gait, balance, and motor persistence. The PANESS will be administered by staff, which has already been trained in PANESS administration. Our team has performed this examination as part of multiple studies. Administration of this measure is approximately 30 minutes.

When possible, the PANESS assessment will be recorded using a device such as a tri-pod mounted video camera. Digital files will be saved to a secure network drive to protect participant privacy. PANESS recordings can be reviewed by multiple personnel to improve precision and accuracy of the assessment and ensure reliability of the scores.

We will correlate the PANESS measurements with ADHD/behavioral symptoms using well established neuropsychological assessments. Thus, we will assess ADHD attention and hyperactive/impulsive symptoms with the DuPaul, BRIEF-2, and TOVA clinical rating tests. Parent symptom ratings are precise and appear to be quite sensitive to change and capture real-world functional change.

### **Psychometric Measures**

All primary measures will first be administered at screening. ***We will use the Response Evaluation in Neurofibromatosis and Schwannomatosis (REiNS) Neurocognitive committee reviewed and recommended assessment tools to assess symptomatology in NF1.*** The length of time required for the child to complete the baseline neuropsychological assessment is estimated to be approximately 90 minutes, including self-report questionnaires. Parent questionnaires can be completed simultaneously while the child is being evaluated and can be completed in about 30

minutes. All neuropsychological assessments that will be used in this study are published tests that have normative data and established reliability and validity for the age range in this study. These tests are all extensively used in clinical and/or research settings. All tests have standardized instructions for administration ensuring there will be no site variation in administration.

To minimize any test-retest effects for neuropsychological outcome measures, alternate forms will be used where possible, to minimize potential practice effects. Furthermore, the use of a placebo group will allow us to identify any potential practice effects and distinguish whether any changes in the treatment group are larger than those accounted by practice effects. In addition, statistical analysis of the data will be conducted to account for confounding variables such as practice effects.

The WISC-V testing is optional for individuals who will not be receiving NAC/Placebo. However, the PANESS and the neuropsychometric testing below will be performed in all “single-visit, non-treatment” participants.

#### DuPaul ADHD-Rating Scale,(ADHD-RS) Home (parent) form $\psi$

This 18 question scale is based on the DSM-5 diagnostic criteria and is widely used in clinical trials and routine care. ***The ADHD-RS rated high in the REiNS committee for assessment of ADHD symptomatology in NF1.*** Administration of this measure is approximately 15 minutes. The ADHD-RS has high internal consistency ( $\alpha>0.90$ ) and good test-retest reliability ( $r=0.85$ ). The rating scale has excellent convergent and discriminant validity.

#### Behavioral Rating Inventory of Executive Function Second Edition (BRIEF-2) $\psi$

***The Behavioral Rating Inventory of Executive Function (BRIEF-2) is a parent-reported symptom rating form that is used regularly in NF1 research and is recommended by the REiNS Neurocognitive Committee for the assessment of executive functions in NF clinical trials.*** This assessment measures executive function behaviors at home and at school for children and adolescents (age 5–18). This scale would give a sense of if any changes are occurring in real-world executive function. The Parent Form is completed by the child’s parent or guardian. It contains 86 items, with eight clinical scales and two validity scales. Behavior descriptors of a child are rated on a three-point Likert scale: “never,” “sometimes,” “always.” Items were developed to capture everyday behaviors associated with executive functions, and tap eight domains including: initiate, inhibit, shift, plan, organize, self-monitor, emotional control, and working memory. These scales are combined to form two broader indices (Behavioral Regulation and Metacognition) and a Global Executive Composite score. Administration of this measure is approximately 15 minutes. The BRIEF-2 has high internal consistency, with a reliability coefficient of 0.90, and good test-retest reliability ( $r=0.82$ ). This measure has well established convergent validity with other measures of behavior and intelligence, and good discriminant validity has been demonstrated against measures of emotional and behavioral functioning.

#### Test of Variables of Attention (TOVA) $\psi$

The TOVA is a computerized, objective measure of attention and inhibitory control normed by gender for ages 4 to 80+. The test is a 22-minute test administered to the participant that provides objective data on response time, inattention, and impulsivity. Test-retest reliability of the TOVA is good, ranging from .74 - .87 with a 1-week interval [66]. The TOVA has also demonstrated good convergent and discriminant validity.

Wechsler Intelligence Scale for Children, Fifth Edition (WISC-V) (ψ optional)

*Working Memory Index.* This index of the WISC-V consists of two scales – Digit Span and Picture Span, which assess auditory and visual working memory in school-aged children. ***This objective measure of working memory has been recommended by the REiNS Neurocognitive Committee (specifically Digit Span) as an outcome measure for working memory in NF clinical trials.*** This is a standardized assessment tool used very frequently in clinical care and clinical research. Administration takes approximately 10 minutes and produces age-referenced standardized scores for each subtest as well as the Index score.

*Processing Speed Index.* This index of the WISC-V consists of two scales – Coding and Symbol Search, which assess processing and response speed in school-aged children. This is a standardized assessment tool used very frequently in clinical care and clinical research. Administration takes approximately 10 minutes and produces age-referenced standardized scores for each subtest as well as the Index score.

The WISC-V has high internal consistency, with reliability coefficients for subtests, primary index scores, and FSIQ ranging from 0.80 to 0.96. It also has good test-retest reliability, with coefficients ranging from 0.80 to 0.94 on subtests, primary indexes, and FSIQ. The WISC-V has high criterion validity and good convergent and discriminant validity.

***We will provide a referral for clinical evaluation to potential participants that receive an ineligible IQ rating (<70)***

*Cognitive Function: Kaufman Brief Intelligence Test, Second Edition (K-BIT-2) ψ*

Each child will be administered a psychological screening battery by trained researchers under the supervision of a licensed psychologist, to assist in evaluation of inclusion and exclusion criteria, and to describe the sample. Within the constraints of limited time and resources, we have selected the following test to evaluate cognitive functioning and learning problems. Participants will undergo a brief IQ screener at baseline using the Kaufman Brief Intelligence Test-2 (KBIT2). The K-BIT-2 has high internal consistency (a ranging from 0.89 to 0.96) and composite test-retest reliability (r=0.90). The measure also has moderate to high correlations for construct and concurrent validity.

***We will provide a referral for clinical evaluation to potential participants that have incidental findings noted in the MRI/MRS***

The Imaging Research Core (IRC) at Cincinnati Children's Hospital will assign a radiologist to review MRI/MRS data and create a report to outline any incidental findings. The incidental finding report is essentially a safety report where the radiologist documents if there are abnormalities separate from their underlying diagnosis. Upon notification of incidental findings, the study team will review the report within 3 business days. The study team will determine whether a clinical referral and/or correspondence with the family is necessary. If the study team determines that the family should be notified (with or without the need for a clinical referral), a member of the study team will contact the family to schedule a call with the study doctor or designee.

***At the study doctor's discretion, we may provide reports or referrals for clinical evaluation to families regarding anxiety and depression assessments***

**Pediatric Anxiety Rating Scale (PARS) [21]**

The PARS is a clinician rated scale that is completed following interview with the parent and child. The PARS has two sections, a symptom checklist and severity items, each of which is linked to the past week. We chose PARS over several possible self-report scales because young children may not be able to complete a self-report scale. Administration of this measure is approximately 10 minutes. The PARS has adequate test-retest reliability (ICC=0.55) and fair internal consistency ( $\alpha=0.64$ ). This scale also has adequate convergent and divergent validity.

**Kiddie Schedule for Affective Disorders and Schizophrenia (K-SADS)**

The KSADS is compatible with the DSM-5 and has been validated in multiple research and treatment settings. The KSADS cross-cutting measure (DSM-5 CC-SM) is an abbreviated version of the extended form. The abbreviated measure is a reliable way to recognize mood, anxiety, psychotic, and disruptive behavior disorders and is a useful screen for eligibility of potential participants. The DSM-5 CC-SM are designed to be self-report measures, completed by the parent and child. The assessment typically is completed in 10 minutes.

**Children's Depression Rating Scale (CDRS) [22]**

The CDRS is a clinician-completed scale that rates presence and severity of depressive symptoms, based on interviews with the parent and child separately. There are 17 behavior items of affective state, rated dimensionally normed for children 6-12 years. Administration of this measure is approximately 10 minutes. The CDRS has good test-retest reliability ( $\alpha=0.86$ ). The scale has a good validity correlation (0.87) and high convergent validity.

**Suicide assessment:**

Per FDA guidance we will screen for Suicidal Ideation and Behavior at each visit. The Columbia Suicide Severity Rating Scale (C-SSRS) is a fast assessment of current and past suicide ideation that is used throughout Cincinnati Children's Hospital. The C-SSRS is administered by a trained researcher and takes approximately 5 minutes to complete.

**Review of anxiety, depression, and C-SSRS responses and referral for clinical evaluation:**

Study doctor (or designee) will verbally administer and then review each suicide assessment. The 'Columbia-Suicide Severity Rating Scale Screen with Triage Points' document outlines the planned course of action based on the participant's response. In particular, if a participant/family discloses any suicide ideation at any point in this study, the study staff will contact the participant's mental health provider or primary care provider and/or *Psychiatric Intake Response Center (PIRC)* at CCHMC for further assessment and guidance within 24 hours.

*The Pediatric Intake Response Center (PIRC) manages psychiatric patient consultation and intake for Cincinnati Children's Hospital Medical Center. Staff members are available 24 hours a day, seven days a week at [contact] or [[contact]](mailto:[contact]).*

### **Rationale for Imaging and Neurophysiology Studies – Overview:**

As an additional secondary endpoint, we will use **TMS and DTI**, because quantitative biomarkers of white matter structures may help measure and predict behavior in NF1 and facilitate interventions into clinical practice. **DTI**, including at least one of its derived parameters, **FA**, shows global changes in NF1 brains which are consistent with white matter dysfunction [11]. In other brain disorders, DTI indices have shown sensitivity to changes after treatment [67-69]. It is clear that white matter properties can also be evaluated using neurophysiological techniques, including Transcranial Magnetic Stimulation. TMS studies are generally brief (30 to 60 minutes), inexpensive, readily repeatable, and do not require sedation. TMS may be helpful for identifying clinically useful, specific brain biomarkers and assessments related to motor and learning difficulties in NF1 and, ultimately, other conditions involving RAS pathways. Specifically, we will test motor system inhibitory physiology (**SICI**), measured using TMS. Preliminary measures in our NF1 population show abnormalities similar to established findings in ADHD obtained in our TMS laboratory at CCHMC.

### **Transcranial Magnetic Stimulation (TMS) $\psi$ :**

Paired pulse TMS will be performed using a Magstim 200R stimulator (Magstim Co., New York, NY, USA) connected through a BistimR module to a 90 mm circular coil. The coil is placed with its center near the vertex in the optimal position and orientation for producing a motor evoked potential (MEP) in the right first dorsal interosseous (FDI) muscle. The electromyogram (EMG) is recorded from the right (or dominant) FDI with surface electrodes, amplified, and filtered (100/1000 Hz) (Coulbourn Instruments, Allentown, PA) before being digitized at 2 kHz and stored for analysis using SignalR software and a Micro1401 interface (Cambridge Electronic Design, Cambridge, UK).

The resting MEP threshold (RMT) is measured using a method similar to that described elsewhere [70] by setting the stimulator to 20 % of maximum output and increasing by 10 % increments until a MEP is obtained. The intensity is then decreased in increments of 1 % of maximum stimulator output until an intensity is reached where 10 averaged stimuli failed to produce a MEP. Active MEP threshold (AMT) is determined by having the participant moderately contract the abductor pollicis brevis with auditory feedback to maintain a constant level of EMG. The stimulator output is decreased in increments of 1 % of maximum output from the RMT until 10 averaged stimuli fail to show a MEP above background.

SICI inhibition is measured in resting muscle with a paired-pulse paradigm using paired vs. single pulse conditions[71]. The first condition is a single test pulse, delivered at an intensity that consistently produces a 500- 1500 mV MEP. In the second condition, a subthreshold stimulus (60% of RMT) is followed after by a test pulse. Twenty trials are performed for the single-pulse condition, and 20 each for the other interstimulus intervals 3 milliseconds (ms), 10 ms. Relative to the single pulse response, the 3 ms interval is inhibitory (SICI) and the 10 ms interval is excitatory (intracortical facilitation). The order of the intervals is varied randomly, and the interval between trials varies randomly by <20% around a mean of 6 seconds. SICI is expressed as a ratio of the mean MEP amplitude after the conditioned pulses divided by the mean MEP amplitude after the single pulses. A detailed review of systems will be obtained before and after TMS, and participants will be provided the number of the investigator and study coordinator to call if there are concerns about possible side effects after the laboratory visit.

### **Magnetic Resonance Imaging (MRI) ψ:**

The MRI protocol will be comprised of un-sedated imaging sequences providing high-resolution detail of brain tissue structure with a primary focus on diffusion FA. A three-dimensional T1-weighted volume will be acquired with 1 mm isotropic resolution and strong contrast between gray matter and white matter tissue. This image volume will be used for anatomic reference and may also serve to explore voxel-level volumetric impact of NF1. A DTI sequence ( $\leq 2$  mm isotropic resolution) will follow, which is directionally sensitive to the rate of water diffusion in brain tissue. This sequence will be designed to measure diffusion rates in 32 or more directions for two or more levels of diffusion weighting (e.g.,  $b = 1000$  s/mm $^2$  and  $2000$  s/mm $^2$ ) to allow voxel-wise determination of not only FA, our primary DTI marker, but also additional microstructural indices that may be sensitive to NF1 and changes with NAC [72, 73]. The DTI data are unique in this study's context in that they are brain-wide: this assessment will be done per voxel, or, alternatively, per predefined white matter Region of Interest (ROI). These additional indices, as well as the potential for regional volumetric assessments, will be exploratory and allow us to address contingencies. DTI will be especially focused on white matter, where restricted diffusion of axonal structures leads to a high degree of anisotropy that reflects tissue integrity.

The T1-weighted image will be processed using one of the commonly available software packages for MRI. Processing will include segmentation into gray matter, white matter, and cerebrospinal fluid tissue types and normalized by transformation into a common spatial template [74]. DTI volumes will have been aligned to each other and with the T1 anatomic image and normalized to the same template space before processing in software to extract FA on a voxel-wise basis. In healthy white matter, diffusion will be greatest along axonal fibers and FA describes the degree to which axial diffusion exceeds transverse diffusion. Besides FA, this processing will provide estimates of mean diffusivity (MD) and the radial (RD) and axial (AD) diffusivities, which have shown changes with NF1 [11, 75, 76] and its treatment [54]. ***Increased FA with decreased RD might suggest improvement in myelin.*** Images may be processed in other ways to extract additional structural information. The T1 segmentations may be analyzed as tissue probability maps for voxel-based morphometry [77]. The DTI data may allow axonal fiber tractography to ascertain structural connectivity between brain regions pertinent to NF1, including tracts of the cingulum and corpus callosum. ***Our primary imaging outcomes in white matter will be voxel-wise comparison of FA between NAC and Placebo groups and regional correlation between FA and neuropsychometric outcomes pre and post-NAC.*** We have healthy reference DTI (FA) data for children 8 to 16 years for comparison to NF1. Since all images will have been normalized to the same space, voxel-wise comparisons of indices across subjects will be possible.

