**Statistical analysis:**

All analysis will be performed with SAS software version 9.4 (SAS Institute Inc., Cary, NC, USA). Spearman's correlation coefficient will be used to evaluate the univariate association between primary outcome (improvement of PANESS scores) and other neurophysiology and brain imaging measurements. Multivariate linear regression model will be used to assess the correlation between the outcomes and the risk factors adjusting for all possible confounders. Model selection criterions such as stepwise method will be employed when necessary. A p-value less than 0.05 will be considered statistically significant.

1. We will assess behavior vs. neurophysiology correlations:

- 1) two-month PANESS change ( $\text{PANESS}_{\text{post-NAC}} - \text{PANESS}_{\text{baseline}}$ ) vs. SICI change ( $\text{SICI}_{\text{post-NAC}} - \text{SICI}_{\text{baseline}}$ ).
- 2) two-month DuPaul change ( $\text{DuPaul}_{\text{post-NAC}} - \text{DuPaul}_{\text{baseline}}$ ) vs. SICI change ( $\text{SICI}_{\text{post-NAC}} - \text{SICI}_{\text{baseline}}$ ).
- 3) two-month BRIEF change ( $\text{BRIEF}_{\text{post-NAC}} - \text{BRIEF}_{\text{baseline}}$ ) vs. SICI change ( $\text{SICI}_{\text{post-NAC}} - \text{SICI}_{\text{baseline}}$ ). Paired t test comparisons of single pulse TMS responses (resulting from pTMS) will be performed to test whether, at each session, single pulse TMS responses differed. The mean single pulse TMS responses for each individual constitute the denominators for the SICI and ICF ratios and need to remain consistent for changes in SICI to be interpretable.

2. We will assess primary behavior (PANESS) vs. neuroimaging correlations:

- 1) two-month PANESS change ( $\text{PANESS}_{\text{post-NAC}} - \text{PANESS}_{\text{baseline}}$ ) vs. Fraction Anisotropy (FA) change ( $\text{FA}_{\text{post-NAC}} - \text{FA}_{\text{baseline}}$ ).

2) two-month PANESS change ( $\text{PANESS}_{\text{post-NAC}} - \text{PANESS}_{\text{baseline}}$ ) vs. MRS GSH change ( $\text{GSH}_{\text{post-NAC}} - \text{GSH}_{\text{baseline}}$ ).

3) two-month PANESS change ( $\text{PANESS}_{\text{post-NAC}} - \text{PANESS}_{\text{baseline}}$ ) vs. MRS GABA change ( $\text{GABA}_{\text{post-NAC}} - \text{GABA}_{\text{baseline}}$ ). The current HERMES method data analysis of MRS can observe GSH concentration changes in the brain of over 20%. We will determine if NAC dose changes GSH in brain and correlates with the primary outcome of study (PANESS).

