For analyses of change over time, mixed models which include subject-specific random effects will be used to account for the correlation of multiple measurements on each subject and capture between-subject variation in rates of change. Unless otherwise noted, the Type I error rate for hypothesis tests and confidence intervals will be controlled at  $\alpha=0.05$ . To assist interpretation, the size of effects of interest in each model will be represented by  $R^2$  (proportion of outcome variation explained by predictors) for linear regression models and/or Cohen's  $d$  (difference in group means, in standard deviation units) for two sample t-tests [81].

Exploratory and descriptive data analysis will precede all inferential analyses to ensure that distributional assumptions are satisfied. In addition to computation of basic descriptive sample statistics (measures of central tendency, variability, and bivariate association), graphical tools such as histograms and scatterplots will be used to assess, e.g., approximate normality, linearity, and presence of influential outlying observations. If substantial violations of parametric assumptions are detected, we will implement non-parametric alternatives, including classical rank-based procedures as well as computationally-intensive sample re-use procedures such as the nonparametric bootstrap. Non-parametric procedures generally have less power than parametric procedures when the assumptions of the latter are met, but often have markedly better properties when the assumptions fail.

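### The primary imaging outcome is a voxel-wise FA comparison between arms, but the only significance rule in the plan is a general p < 0.05 with no correction for the number of voxels

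*Combined protocol and SAP*

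**What the plan says.** The Magnetic Resonance Imaging (MRI) section of the combined protocol and SAP names the main imaging contrast: "Our primary imaging outcomes in white matter will be voxel-wise comparison of FA between NAC and Placebo groups". It pairs this with regional correlations between FA and the neuropsychometric outcomes. Earlier in the same section the unit of analysis for the diffusion data is left open: "this assessment will be done per voxel, or, alternatively, per predefined white matter Region of Interest (ROI"). No regions are listed or counted at that point.

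The overview of the imaging and neurophysiology rationale places DTI in the trial's hierarchy with the words "As an additional secondary endpoint, we will use". FA is therefore primary among the imaging measures and secondary in the trial.

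The Statistical analysis section gives one decision rule, "A p-value less than 0.05 will be considered statistically significant", and later adds: "Unless otherwise noted, the Type I error rate for hypothesis tests and confidence intervals will be controlled at" 0.05. Nothing different is noted for imaging. FA appears in that section only under the item "We will assess primary behavior (PANESS) vs. neuroimaging correlations", as PANESS change against FA change. The voxel-wise comparison between arms is not described there. The bootstrap is offered for violated distributional assumptions, not for multiplicity.

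**The concern.** A voxel-wise comparison is tens of thousands of tests, one per location. A rule that is adequate for a single test flags about one location in twenty when there is no effect. The plan names such a comparison as its leading imaging outcome and supplies no threshold suited to it, so the only rule a reader can apply is the general one.

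At stake is the reading of the FA result. Under the default, a map with flagged white-matter voxels is what one expects from an inactive treatment, so it could not be told apart from evidence that NAC changes white matter. If the correction, mask and threshold are instead chosen once the maps have been seen, the result depends on choices that a pre-specified plan should have fixed. The FA part of the third secondary aim rests on this comparison.

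**Working it through.** **1. The plan's own figure.** The documents give no error rate or power for the FA maps. The one figure to reproduce is the trial's sample size (Determination of sample size): 26 per group, effect size 0.8, two-sided 0.05, stated power 81%. The noncentral t distribution with 50 degrees of freedom gives 80.7%, and 52 / 0.9 = 57.8, rounded up to 58. Both reproduce. The 26 per arm is used in step 4.

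**2. Inputs for the voxel count.**
- Voxel size: 2 mm isotropic or finer (MRI section), so at most 2 × 2 × 2 = 8 mm³.
- Threshold: p < 0.05 (Statistical analysis).
- White-matter volume: not in the documents. Assumed to be 200 to 600 mL.

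**3. Expected false positives when NAC has no effect.** Voxels = volume / voxel volume. Expected false positives = 0.05 × voxels.

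| Assumed volume tested | Voxels at 2 mm | Expected false positives |
|---|---|---|
| 50 mL | 6,250 | about 310 |
| 100 mL | 12,500 | 625 |
| 200 mL | 25,000 | 1,250 |
| 400 mL | 50,000 | 2,500 |
| 600 mL | 75,000 | 3,750 |

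Finer voxels raise the count. For 200 to 600 mL it is 2,963 to 8,889 at 1.5 mm and 10,000 to 30,000 at 1 mm. An expected count of 1,000 at 2 mm needs 160 mL (160,000 / 8 × 0.05 = 1,000).

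**4. Does spatial smoothness rescue the rule?** Correlation between neighbouring voxels does not change the expected count; it changes only the spread. A null simulation used 26 per arm, a mask of 50,192 voxels of 2 mm, a two-sided t-test at each voxel and 120 runs per setting.

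| Smoothing (FWHM) | Mean false voxels | Central 95% of runs | Runs with at least 2,000 |
|---|---|---|---|
| none | 2,509 | 2,406 to 2,609 | 100% |
| 6 mm | 2,522 | 2,086 to 2,888 | 99% |
| 8 mm | 2,537 | 2,075 to 3,136 | 99% |
| 12 mm | 2,499 | 1,669 to 3,616 | 87% |

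Every run at every setting had at least 1,000 false-positive voxels. As a cruder check, suppose the map amounts to only 50 or 100 independent tests (an assumption). The chance of at least one false positive is then 1 − 0.95^50 = 92% or 1 − 0.95^100 = 99.4%.

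**5. What a corrected threshold looks like.** In the same simulation, holding the chance of any false voxel at 5% needed |t| of about 5.1 to 5.7, depending on smoothness. The uncorrected rule needs 2.01. Bonferroni over 50,000 voxels would need p < 0.05 / 50,000 = 0.000001.

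**6. The region alternative.** Regions would remove the large counts but not the problem, because no correction is stated for them either. If 20 or 48 independent regions are assumed, the chance of at least one false positive is 1 − 0.95^20 = 64% or 1 − 0.95^48 = 91%.

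**The case against.** The strongest reply is that the plan is silent here, not wrong. The p < 0.05 sentence closes a paragraph on Spearman correlation, regression and stepwise selection in SAS. It is never tied to the voxel maps, which are assigned to unnamed imaging software. A family-wise-corrected 0.05 would be compatible with every sentence quoted above, and an imaging analyst may well apply one. This stands in part. A reader might infer that the investigators have chosen uncorrected voxel-wise testing, and the documents do not support that. They do, however, offer no other rule, and following them as written gives the result in the working.

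Second, the counts rest on an assumed white-matter volume, and a small mask or a region analysis would give far fewer. This also stands. A reader might infer that thousands of false voxels, or a positive finding, are guaranteed. The documents give neither a volume nor a mask, so the count is conditional and the right word is near-certain.

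Third, the scope is limited. A reader might infer that error control fails for the whole of the third secondary aim, or for the trial. That aim also covers GSH and GABA from spectroscopy, which are not voxel-wise tests, and the PANESS analysis does not depend on FA.

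Fourth, the voxel-or-region choice is less open than it looks, since the later statement in the MRI section settles on voxels for the group contrast and regions for the correlations. That is fair, but neither analysis has a stated correction.

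Finally, some pages directly after the statistical text were not in the material reviewed, so the absence of a correction can be claimed only for the text available.

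**Conclusion.** The point holds as a gap whose literal filling fails. The plan makes a voxel-wise comparison of FA between arms its primary imaging outcome and gives only a general p < 0.05 rule. Under that rule about 5% of the voxels tested are expected to be flagged with no treatment effect. The size in voxels rests on the assumed 200 to 600 mL at 2 mm, but the 5% share and the near-certainty of some false positives do not depend on that volume. The nominal 0.05 error rate would not hold for the FA group comparison. Because DTI is a secondary endpoint, this should be corrected but does not threaten the trial's main result or its sample size.

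**What to change.** In the MRI and Statistical analysis sections, state that the between-arm comparison of voxel-wise FA change is judged at family-wise-error-corrected p < 0.05 within a pre-specified white-matter mask. Use permutation with threshold-free cluster enhancement or a pre-specified cluster-forming threshold. Permute arm within the randomisation strata actually used. The two Randomization sections must first be reconciled: the earlier one stratifies by ADHD, age and sex, the later one (under Data Analysis/Methods) by sex and ADHD only.

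Alternatively, pre-specify a short list of white-matter regions as the primary imaging test with Holm correction, and label the voxel-wise maps descriptive. The cingulum and corpus callosum are candidates, but the MRI section mentions them only as possible tractography targets, so they would have to be newly named as FA regions.

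For the regional correlations between FA and the neuropsychometric outcomes, apply Holm or false-discovery-rate control across the region-by-test pairs, or label them exploratory.

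Either route needs a few sentences of text and a standard software option, with no extra participants, scans or visits. The cost is lower sensitivity than uncorrected maps.
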